#### **b. Procedure Risks**

The research procedures outlined in this protocol comply with published protocols for clinical trial and functional imaging research, which have been developed to maximize subject safety. Following these principles, we will minimize as much as possible the risk, consistent with sound research design and good clinical practice, in the following ways:

##### **1. Screening for Contraindications:**

Participants will be extensively screened for all contraindications of treatments and assessments. During screening, participants' eligibility will be established based on a full psychiatric (psychiatric and medication history, diagnostic interviews, and self-report assays to assess all areas that might put participants at risk including history or presence of mania, suicidality, and alcohol and drug abuse) and medical screening (medical history, physical exam, blood and urine tests to assess all issues that might put participants at risk including epilepsy, heart, kidney, and liver function, likelihood of drug use, and pregnancy).

##### **2. Safety Monitoring Plan:**

A data and safety monitoring plan will be established, and the proposed study will be registered as a clinical trial on clinicaltrials.gov.

##### **3. Adherence to Treatment Guidelines:**

The treatment protocol uses parameters described in Butterfield et al. (Psychiatry Research, 2016) in adults with ADHD.

##### **4. Monitoring During the Study:**

Participants will be monitored regularly for treatment side effects and any health status changes that might put them at risk. Participants will be monitored every week for side effects generally and also specifically (i.e., with quantitative scales) for mood changes and suicidality. All significant changes described by participants and/or measured in the scales will be recorded in the patients' case report forms, immediately reported to prescribing psychiatrists (in case data were collected by other research personnel), and all necessary actions will be taken for participants' safety and well-being. Participants will be reminded and reassessed for the following:

- Use of birth control (females of childbearing potential),
- Alcohol and drug abstinence, and
- Changes to current medications.

**5. Trained Personnel:**

The study will be conducted by experienced lead investigators and appropriately trained research personnel. All study research personnel will be adequately and appropriately trained with regard to general guidelines for research with human subjects.

[name], M.D., Ph.D. and [name], M.D., Ph.D. has extensive experience in clinical trials involving drug treatments for mood disorder patients. All study procedures will be detailed in the study's manual of standard operating procedures (MOP), and personnel will be required to act according to those. The study's manual will include, among others, a safety plan for reporting suicidality during screening and monitoring, safety procedures for MRI testing, and recognition and reporting of adverse events (AEs) and serious adverse events (SAEs).

---

**c. Use of Deception in the Study**

Deception will not be used in this study.

---

**d. Use of Audio and Video Recordings**

No audio or video recordings will occur during the study.

---

**e. Alternative Procedures or Courses of Treatment**

There are currently no standard-of-care medications available that specifically target or treat cognitive impairment in depression. Initiation of antidepressant medication, particularly serotonin selective reuptake inhibitors (SSRIs), the first-line treatment for major depressive disorder, may be advantageous to participants. SSRIs typically take a minimum of 6-8 weeks once titrated to therapeutic dose to show therapeutic benefit with regard to symptoms. There are risks associated with SSRI treatment including medication side effects such as nausea, gastrointestinal side effects, increased anxiety, headaches, dizziness, fatigue, and a Black box warning of increasing risk of suicidal ideation in adolescence and young adulthood.

Electing to participate in the current study will delay initiating a trial of SSRI treatment by 6 weeks, but participants will then be able to continue with first-line therapy upon study completion. This information will be disclosed in the consenting process and form as standard-of-care drug.

---

**f. Will it be possible to continue the more (most) appropriate therapy for the participant(s) after the conclusion of the study?**

Upon completion of Week 8 of the treatment period, participants will have the choice of whether they would prefer to continue on the treatment or be tapered off the drug by the study MD during Weeks 9 and 10. To maintain the blind, participants who would like to continue treatment will be cross-titrated or down-titrated on their assigned medication (placebo or guanfacine) while simultaneously up-titrating on guanfacine.

Participants must have a physician willing to prescribe them guanfacine upon termination of the study and provide a note from their physician to the study clinician, or they will be tapered off the drug over the two-week safety phase. Upon request, a letter will be written to notify the physician of the participant's involvement in the study. This would facilitate the option for participants' usual care physician to continue treatment with GIR as part of their ongoing care of the participant after completion of the study.

---

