**a. Procedures**

1. Recruitment and screening: Participants experiencing depressive symptoms and not taking any psychiatric medications as determined by a 5 half-life wash out period will be recruited from the community, including students and employees at Stanford. Recruitment will come primarily from Facebook ads, which will use only IRB approved material. A flyer will also be physically posted on boards in public locations in order to include a variety of sources for the study.
2. Individuals will need to participate in 3 screening visits in order to enroll in the study. During the first visit, participants will review informed consent, be administered a clinical interview, and be sent instructions for completing cognitive testing at home.
3. If eligibility after this initial screening visit, the second visit will be a medical screen in order to ensure participants are safe to take GIR and will include standard blood tests, medical history, vitals, and a urine drug test.
4. If the participant meets medical and cognitive criteria, functional magnetic resonance imaging (fMRI) scans will be undertaken at another study visit at The Stanford Center for Cognitive and Neurobiological Imaging (CNI). Using a participant's task-evoked activity

in the dorsolateral prefrontal cortex (dLPFC) and performance on objective cognitive testing, we will apply thresholds using established healthy norms to select participants within the cognitive biotype+ group.

5. Participants will receive GIR for a period of 8 weeks sent to their place of residence from Mariner pharmacy.
6. Participants will be seen in-person or virtually by a study clinician at weeks 2, 4, 6, 8, and 10 and an appropriately trained clinical research coordinator at weeks 1, 3, 5, 7, and 9. All subjects will have an fMRI scan after 6-8 weeks of taking GIR. During in-person visits and virtual monitoring, we will assess participants for the following: changes to symptoms, function, and suicidality, adherence to GIR, changes to concomitant medication(s), adverse events (AEs), birth control usage compliance, likelihood of pregnancy (female participants of childbearing potential), and vital signs if appropriate.

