**g. Study Endpoint(s)**

The endpoint for primary and secondary measures will be 8 weeks after initiation of GIR or placebo, regardless of the study outcomes. Additional measures will be collected at the final endpoint of 10 weeks. If a subject reports a significant adverse event or worsening depression, the participant will be removed from the study. The study will not be terminated prematurely in the event that participants randomized to GIR have greater improvement than participants randomized to placebo.

---

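### The protocol puts the delay in starting an SSRI at 6 weeks, but its own schedule gives at least 8 weeks, and 10 if completion means the final endpoint

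*Protocol*

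**What the plan says.** Protocol section 2.e (alternative treatments) acknowledges that starting an SSRI might benefit participants. It then states that electing to take part "will delay initiating a trial of SSRI treatment by 6 weeks", adding that "participants will then be able to continue with first-line therapy upon study completion". The next sentence reads: "This information will be disclosed in the consenting process and form as standard-of-care drug".

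The schedule is set out in other sections:

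- Section 2.a, item 5: "Participants will receive GIR for a period of 8 weeks".
- Section 2.a, item 6: "All subjects will have an fMRI scan after 6-8 weeks of taking GIR". The same item lists clinician visits through week 10.
- Section 2.f: after week 8, participants either continue on guanfacine, provided a physician will prescribe it, "or they will be tapered off the drug over the two-week safety phase". That phase is weeks 9 and 10.
- Section 2.g: "The endpoint for primary and secondary measures will be 8 weeks after initiation of GIR or placebo", and "Additional measures will be collected at the final endpoint of 10 weeks".
- Section 8.m: individual participation lasts about 12 weeks, of which 8 are the treatment phase.

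**The concern.** Section 2.e ties the end of the delay to completion of the study. Nothing in the schedule lets a participant complete at week 6. The 6-week figure therefore conflicts with the schedule, and it errs on the side that makes participation look less burdensome.

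This is the only place where the protocol puts a number on how long first-line treatment is postponed. The participants concerned enter with an HDRS-17 score of 14 or more (section 8.h). The following sentence says the information is meant for the consent process. If the figure is carried over, people weighing an SSRI against the trial would be given too short a delay.

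The effect also carries through to the expected time to benefit. Section 2.e says an SSRI needs at least 6 to 8 weeks at therapeutic dose before it helps, and that wait comes on top of the delay in starting.

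**Working it through.** This is calendar arithmetic on the protocol's own schedule, counted from first dose.

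**Inputs**

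| Item | Value | Protocol section |
|---|---|---|
| Stated SSRI delay | 6 weeks | 2.e |
| Point at which the delay ends | study completion | 2.e |
| Time on study drug | 8 weeks | 2.a, item 5 |
| Primary and secondary endpoint | week 8 | 2.g |
| Safety phase (taper or continuation) | 2 weeks (weeks 9 and 10) | 2.f |
| Final endpoint | week 10 | 2.g |
| Follow-up scan | weeks 6 to 8 | 2.a, item 6 |
| Follow-up scan, as described for payment | week 8 | 8.k |
| Whole enrolment | about 12 weeks | 8.m |

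**Can the 6 weeks be reproduced?** The nearest on-treatment milestone is the early edge of the scan window. A scan at week 6 is an assessment and does not complete the study: dosing and the main endpoint run to week 8 and clinician visits to week 10. Section 8.k also places this scan at week 8. Section 2.e does mention 6 to 8 weeks just before the delay, but there it is the time an SSRI takes to work once titrated, not the time before one can be started. No reading of study completion gives 6 weeks.

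**Shortfall = scheduled duration − stated delay**

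- End of treatment: 8 − 6 = 2 weeks, and 2/8 = 25% of the true duration.
- Final endpoint: 8 + 2 = 10 weeks; 10 − 6 = 4 weeks, and 4/10 = 40%.
- Whole enrolment: about 12 − 6 = about 6 weeks. This is shown for context only, because it is not counted from first dose.

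**Time to expected SSRI benefit = delay + 6 to 8 weeks at therapeutic dose** (SSRI titration time would be added to each line)

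- As stated: 6 + 6 = 12 to 6 + 8 = 14 weeks.
- From end of treatment: 8 + 6 = 14 to 8 + 8 = 16 weeks.
- From the final endpoint: 10 + 6 = 16 to 10 + 8 = 18 weeks.

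**The case against.** Five points can be made on the other side.

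1. **No explicit on-study ban on SSRIs.** Current psychotropic use is an entry exclusion (section 8.h); during the study the text speaks only of monitoring medication changes. That an SSRI cannot start before week 8 is thus an inference. It is a strong one, because section 2.e itself makes first-line therapy available on completion and the main endpoint is at week 8. For weeks 9 and 10 the silence matters more, which is why the 4-week gap is conditional.

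2. **The starting point.** Section 2.e counts from the decision to participate, which comes before first dose. Three screening visits, a possible washout of five half-lives (section 8.h) and the roughly 12 weeks of enrolment in section 8.m all lengthen the delay. This is correct, and it means that counting from first dose is conservative. It does not rescue the 6 weeks.

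3. **The consent form is unseen.** The sentence about disclosure is awkwardly worded, so it is not certain that the 6-week figure itself is carried over. This stands: a misstatement to participants is a possibility, not something shown.

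4. **Participants are not locked in.** They may stop at any time (section 9.c) and are removed if depression worsens (section 2.g). This also stands, but it shortens the delay only for people who leave. It does not make 6 weeks right for those who complete.

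5. **The correct schedule appears elsewhere.** Staff and the IRB are unlikely to run or approve a 6-week study because of one sentence. This limits the practical harm but does not remove the inconsistency.

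**Conclusion.** The concern holds: the 6-week figure is wrong as written. For a participant who completes the 8 weeks of study drug it is short by 2 weeks, given section 2.e's own premise that first-line therapy waits until the study is complete. If completion means the week-10 final endpoint, as the wording suggests, it is short by 4 weeks; that depends on the unstated rule for SSRIs in weeks 9 and 10. Both gaps are counted from first dose, so time before dosing would only add to them.

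This is a matter of disclosure and internal consistency. It should be corrected because it is the protocol's only figure for the postponement of first-line treatment. It has no bearing on the sample size, the endpoints or the analysis.

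**What to change.** The sponsor should first decide whether an SSRI may be started during weeks 9 and 10, then amend section 2.e to match:

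- If it may not, replace 6 weeks with about 10 weeks from first dose.
- If it may, write at least 8 weeks from first dose and state the permission explicitly.

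Naming first dose as the starting point keeps the figure distinct from the roughly 12 weeks of enrolment in section 8.m. The consent form should be checked and made to carry the same figure.

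The cost is one decision, one changed number in the protocol and, if it repeats there, one in the consent form, submitted through the IRB. The stated burden becomes somewhat less favourable. No treatment rule needs to change.

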**g. Study Endpoint(s)**

The endpoint for primary and secondary measures will be 8 weeks after initiation of GIR or placebo, regardless of the study outcomes. Additional measures will be collected at the final endpoint of 10 weeks. If a subject reports a significant adverse event or worsening depression, the participant will be removed from the study. The study will not be terminated prematurely in the event that participants randomized to GIR have greater improvement than participants randomized to placebo.

---

**3. BACKGROUND**

---

**a. Past Experimental and/or Clinical Findings**

A single mechanism is unlikely to underlie a broad descriptive diagnosis such as depression. Thus, our approach is anchored by a neural-circuit taxonomy that proposes distinct biotypes of depression derived from functional magnetic resonance imaging (fMRI) (Williams, Lancet Psychiatry, 2016; Williams, Depress. Anxiety, 2017).

One of these circuits is the cognitive control circuit, which has been delineated by the PI and others in human neuroimaging work to comprise the dorsolateral prefrontal cortex (dLPFC) and its projections to the dorsal parietal cortex and anterior cingulate cortex. This circuit is engaged by cognitive control tasks requiring selective attention and inhibition, such as the Go-NoGo and Continuous Performance N-back tasks.

Related neuroimaging indicates that a subset of people with depression is characterized by dLPFC hypoactivation and cognitive impairments. These cognitive symptoms result in substantial morbidity and disability in individuals struggling with depression and are a principal determinant of quality of life and function, including workforce productivity, suggested to contribute more than 60% of MDD-related economic burden.

A meta-analysis of 13 studies comparing cognitive function in first-episode MDD subjects with healthy control participants found that depressed patients had significant impairments in psychomotor speed, attention, and most aspects of executive function (including attentional switching, verbal fluency, and cognitive flexibility). A substantial subset of these patients (approximately 20%) exhibited cognitive deficits of two standard deviations below the mean on two or more cognitive domains. These patients also appear to be poor responders to standard antidepressants (Lee et al. Journal of Affective Disorders 2012, Gualtieri et al., Journal of Clinical Psychiatry 2008). Thus, there remains a critical need to find effective treatments for this subset of MDD patients.

Cognitive dysfunction greatly contributes to the ongoing burden of disability and functional impairment in MDD after mood symptoms attain remission (McIntyre et al.,

Journal Anxiety and Depression, 2013). Our research group has previously reported results of the International Study to Predict Optimized Treatment in Depression (iSPOT-D) trial, a randomized controlled study investigating the effects of three different antidepressant medications in 1008 depressed patients. These patients demonstrate ongoing impairment in five domains of cognitive function – attention, response inhibition, verbal memory, decision speed, and information processing – after 8 weeks of antidepressant medication treatment, irrespective of the antidepressant treatment group, including patients who attained remission based on clinical outcome measures (Shilyansky et al., Lancet Psychiatry, 2016).

Guanfacine is an  $\alpha$ 2A-adrenergic receptor agonist that has been shown to selectively facilitate plasticity in frontal norepinephrine pathways. In preclinical studies, guanfacine binds more preferentially to postsynaptic  $\alpha$ 2A-adrenergic receptors than clonidine. Preclinical studies and clinical trials indicate that guanfacine acts directly by enhancing noradrenaline functioning via  $\alpha$ 2A-adrenoceptors in the PFC, primarily at postsynaptic receptors, through inhibition of cyclic adenosine monophosphate, closing hyperpolarization-activated cyclic nucleotide-gated channels, modulating synaptic functioning, and strengthening PFC-network connectivity, thereby improving PFC cognitive functions.

---

**b. Findings from Past Animal Experiments**

Over three decades of animal research has demonstrated that working memory can be improved by alpha-2-adrenoceptor agonists such as guanfacine, while infusions of alpha-2 antagonists into the PFC impair working memory (Arnsten et al., 1988; Arnsten and Goldman-Rakic, 1985; Franowicz and Arnsten, 1998; Rama et al., 1996; Ramos et al., 2006; Tanila et al., 1996; Wang et al., 2007). Furthermore, animal studies show that guanfacine has robust antidepressant effects and can reverse a depression-like state induced by cholinergic signaling (Minuer et al., 2015). In particular, both acute and chronic guanfacine administration decreased immobility time of mice in the forced swim test.

---

**4. RADIOISOTOPES OR RADIATION MACHINES**

---

**a. Standard of Care (SOC) Procedures**

Identify Week/Month of Study	Name of Exam	Identify if SOC or Research
NA	NA	NA

---

**b. Radioisotopes**

i. Radionuclide(s) and chemical form(s)

NA

ii. Total number of times the radioisotope and activity will be administered (mCi) and the route of administration for a typical study participant

NA

iii. If not FDA approved: dosimetry information and source documents (package insert, Medical Internal Radiation Dose [MIRD] calculation, and peer reviewed literature)

NA

---

**c. Radiation Machines – Diagnostic Procedures**

i. Examination description (well-established procedures)

NA

ii. Total number of times each procedure will be performed (typical study participant)

NA

iii. Setup and techniques to support dose modeling

NA

iv. FDA status of the machine and information on dose modeling (if procedure is not well-established)

NA

---

**d. Radiation Machines – Therapeutic Procedures**

i. Area treated, dose per fraction/number of fractions, performed as part of normal clinical management or due to research participation (well-established procedures)

NA

ii. FDA status of the machine, basis for dosimetry, area treated, dose per fraction and number of fractions (if procedure is not well-established)

NA

---

**5. DEVICES USED IN THE STUDY**

---

**a. Investigational Devices (Including Commercial Devices Used Off-Label)**

Investigational Device 1	
Name:	Sigma MR750 3T scanner
Description:	The MR research being conducted requires highly specialized equipment and imaging software that does not exist in the clinical MR market, so it is designed and manufactured by researchers at the Lucas Center and other hardware companies.
Significant Risk? (Y/N)	Yes
Rationale for Non-Significant Risk	Although some of the imaging software and equipment are not FDA approved, they have been tested for safety and are very similar to what is used regularly in clinical MR examinations. The MR personnel are highly trained in the set-up, utilization, and monitoring of this equipment.
Investigational Device 2	
Name:	GE 3 Tesla Ultra-High Performance (UHP) scanner
Description:	The MR research being conducted requires highly specialized equipment and imaging software that does not exist in the clinical MR market so it is designed and manufactured by researchers at the Lucas Center and other hardware companies.
Significant Risk? (Y/N)	Yes

Rationale for Non-Significant Risk	
The 3T UHP scanner from GE is an upgrade to the 3T MR750 which was a commercial FDA-approved system. The UHP system utilizes many components from GE's 3T Signa Premier, including gradient drivers, power supply, transmit and receive system electronics, but uses a higher performance gradient coil. The 3T UHP system is not FDA approved, and is subject to the 21 CFR 812 investigational device(IDE) regulations as well as 21 CFR 50 and 56. The system has been tested by GE according to UL606001-1 and also for compliance with IEC 60601-2-33 (ed 3.1) -- meeting limits and guidelines for peripheral nerve stimulation, patient thermal, SAR limit, acoustic noise, flammability rating UL94-5VA for safety covers, hydrostatic pressure, electrical hazards, dielectric strength and pinch point. The MRI scans in this study will also utilize operational parameters within FDA guidelines for Nonsignificant Risk thus an Investigational Device Exemption (IDE) from FDA should not be necessary. In addition, the MR research being conducted requires highly specialized software that does not exist in the clinical MR market so it is designed and implemented by researchers at the CNI. Any such software will be considered investigational, will function as a nonsignificant risk device, and is subject to the 21 CFR 812 investigational device (IDE) regulations as well as 21 CFR 50 and 56. The investigational image acquisition software will conform to FDA guidelines for MR safety related to heating (SAR), peripheral nerve stimulation (dB/dt), and acoustic noise.
 
 
- The scanner is for investigational use only and will not be used in to diagnose, cure, treat or prevent the impairment of human health. Additionally, the magnet has been tested by GE and meets the limits and guidelines for peripheral nerve stimulation, patient thermal, SAR limit, acoustic noise, flammability rating UL94-5VA for safety covers, hydrostatic pressure, electrical hazards, dielectric strength and pinch point according to medical equipment and flammability standards.
 
- The MRI scans in this study will utilize operational parameters within FDA guidelines for Nonsignificant Risk, same as before the upgrade.
 

------------------------------------	--

---

